#### 5. Handling Missing Data

- If  $< 5\%$  missing on any outcome, complete-case analysis.
- If  $\geq 5\%$ , multiple imputation by chained equations (20 imputations), including all baseline covariates and outcomes in the imputation model.
- Sensitivity analyses: per-protocol (participants attending  $\geq 75\%$  of sessions).

#### 6. Safety Analyses

- **Adverse events:** Number and proportion of participants experiencing any AE and serious AE in each arm.
- Comparison by arm via  $\chi^2$  tests; descriptively summarised by severity and relatedness.

#### 7. Interim Analyses

- No formal interim efficacy analyses planned (feasibility pilot).
- Safety data reviewed by independent Data Monitoring Committee at mid-point (after 50% of participants complete Week 8).

All analyses will be implemented in R (version  $\geq 4.0$ ), with scripts and output archived for reproducibility.

#### Qualitative Analysis

- **Thematic analysis** of open-text questionnaire feedback, following Braun & Clarke's framework.
- Coded and analysed using **NVivo or MAXQDA**.

## STUDY PROTOCOL

## ReHabGame: A Markerless, Game-Based Rehabilitation Program

### 1 BACKGROUND

Stroke, traumatic brain injury, multiple sclerosis, and musculoskeletal (MSK) shoulder disorders (e.g., rotator cuff repair, adhesive capsulitis, arthroplasty) all lead to significant upper-limb impairment, reduced independence, and diminished quality of life (World Health Organization [WHO], 2021). Traditional rehabilitation for these conditions relies on therapist-guided exercises, often repetitive, time-consuming, and subject to variability in delivery and patient adherence. As a result, many patients fail to achieve their full recovery potential, and therapists are constrained by limited time and resources (Laver et al., 2017).

In recent years, game-based rehabilitation systems have gained attention for their potential to boost patient engagement and foster more frequent, high-quality practice (Maier et al., 2019). These systems use interactive, often motion-capture technology to guide and track movements in real-time, turning therapy into a more enjoyable and rewarding experience. Research suggests that virtual or augmented environments can encourage patients to perform more repetitions and challenge themselves in ways that traditional exercises may not (Cameirão et al., 2010).

Over the last decade, various technologies have emerged as promising tools for delivering objective, repeatable, and engaging exercise programs without the need for wearable sensors or complex setup (Maier et al., 2019). Gamified rehabilitation platforms leverage these technologies to transform therapeutic exercises into interactive games. It has the potential to provide real-time feedback, adaptive difficulty, and motivational elements (scores, levels, and visual rewards) that can enhance patient engagement and long-term adherence.

ReHabGame is a markerless, game-based rehabilitation system that integrates Kinect-derived motion tracking with a bespoke adaptive algorithm to tailor exercise difficulty in real time. In this study we designed a two-cohort, two-arm RCT comparing **Combined ReHabGame + usual care** versus **usual care alone**, in both neurological and MSK cohorts. By stratifying participants and blinding outcome assessors, this study will determine the added value of ReHabGame when combined with usual care, characterize feasibility metrics (recruitment, retention, adherence), and generate robust data on functional gains, pain modulation, and motion-tracking validity.

### 2 RATIONALE

Upper-limb impairments from neurological injuries (e.g., stroke, traumatic brain injury, multiple sclerosis) and musculoskeletal (MSK) shoulder disorders (e.g., rotator cuff repair, adhesive capsulitis, shoulder arthroplasty) both lead to profound limitations in daily function, independence, and quality of life. However, traditional rehabilitation—whether neuro-focused or MSK-focused—relies heavily on therapist-led, repetitive exercises that can be monotonous, resource-intensive, and subject to variable patient adherence.

Markerless motion-capture and gamification offer a compelling solution:

- Objective feedback: Systems like Microsoft Kinect accurately track joint movement and repetition counts without wearable sensors, reducing setup burden and allowing precise, real-time performance metrics.
- Adaptive challenge: A game-based interface can dynamically tailor exercise difficulty to a patient's current ability, minimizing boredom or frustration and promoting "just-right" challenge.
- Motivation & engagement: Visual rewards, scoring, and level progression have been shown to increase session attendance, enjoyment, and long-term adherence, key factors in driving neural plasticity and tissue remodelling.

Evidence gaps remain, however:

- Lack of rigorous RCTs directly comparing game-based therapy to standard physiotherapy, particularly in MSK populations.
- Unknown additive effects of combining gamified and conventional therapies, clinics often offer "usual care" alongside any novel intervention, but the independent contribution of each is rarely isolated.
- Population differences: Neurological and MSK conditions exhibit distinct pathophysiology (e.g., motor control deficits versus pain-limited range of motion and tendon loading), yet few studies have contrasted gamified rehab across these cohorts within the same trial.

By conducting a two-cohort, two-arm randomized controlled trial, we will:

- Determine whether **Combined ReHabGame + usual care** produces greater gains than **usual care alone** in both cohorts.
- Assess whether a combined approach affords additive benefits
- Evaluate feasibility, recruitment, retention, adherence, and usability metrics within each cohort.
- Generate cohort-specific data on functional recovery (e.g., FMA-UE, SPADI), pain modulation, and motion-tracking validity, addressing both motor control and musculoskeletal loading concerns.

This design ensures robust, clinically relevant evidence to guide the optimal deployment of gamified rehabilitation, whether as an adjunct to clinic sessions, or an integrated component of standard care, across diverse patient populations.

### 3 THEORETICAL FRAMEWORK

Our study draws on motor learning principles and motivational theories to explain how a game-based rehabilitation approach can enhance arm function in individuals with motor impairments:

#### Motor Learning Theory

- Emphasizes repetition, feedback, and task-specific practice as key elements for improving movement control.

- ReHabGame provides repetitive, goal-directed exercises in a virtual environment, allowing participants to practice functional movements repeatedly with real-time feedback.

### Self-Determination Theory (SDT)

- Highlights autonomy, competence, and relatedness as core motivational drivers.
- By offering engaging tasks and immediate success indicators (e.g., scores or visual cues), ReHabGame can foster a sense of achievement (competence) and empower users to choose when and how they practice (autonomy).

### Gamification and Engagement

- Incorporates game design elements—such as points, levels, and challenges—to boost motivation and adherence.
- The interactive nature of ReHabGame can make repetitive exercises more enjoyable, reducing the boredom often associated with traditional rehab.

### Markerless Technology for Accessibility

- Traditional motion-capture systems often rely on markers or complex hardware, limiting widespread use.
- A markerless approach aligns with research suggesting that accessible, easy-to-use technology can expand rehabilitation opportunities to more diverse settings and populations.

By integrating these concepts—motor learning, self-determination, gamification, and accessible technology—ReHabGame addresses gaps identified in the Background (e.g., low engagement, limited practicality) and provides a robust framework for studying how a virtual, game-based system can facilitate upper-limb recovery.

## 4 RESEARCH QUESTION/AIM(S)

To determine the added benefit of Combined ReHabGame + usual care versus usual care alone on upper-limb function, pain, and usability in two cohorts (Neurological and MSK).

### 4.1 Objectives

#### Primary Research Questions

##### 1. Neurological cohort:

- Does Combined ReHabGame + usual care produce greater improvement in upper-limb motor control (FMA-UE, baseline→Week 8) compared to usual-care alone?

##### 2. MSK cohort:

- Does Combined ReHabGame + usual care produce greater improvement in shoulder pain and function (SPADI, baseline→Week 8) compared to usual-care alone?

## Secondary Research Questions

Within each cohort, how do the two arms compare on:

- **Functional independence:** Barthel Index (Neurological) or DASH (MSK)
- **Engagement & usability:** System Usability Scale (SUS) scores and engagement survey ratings at Weeks 4, 8, 12
- **Session adherence:** Number and proportion of prescribed sessions completed
- **Motion-tracking performance:** Changes in Kinect-derived metrics (range of motion, smoothness, accuracy)
- **Pain & ROM (MSK only):** Pain VAS and goniometric ROM

## Exploratory Aims

1. Compare **cost and resource utilization** (therapist time, equipment) across arms.
2. Identify **barriers and facilitators** to adoption of gamified rehabilitation via participant interviews.
3. Assess **safety outcomes** (adverse events, overuse symptoms) and determine whether combined therapy introduces any incremental risk.

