## Planned Statistical Analyses

All analyses will be conducted **separately within each cohort** (Neurological and MSK), by original randomised allocation (intention-to-treat). Two-sided tests with  $\alpha = 0.05$  will be used throughout.

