#### Analysis:

- Continuous outcomes → ANCOVA as above.
- Repeated measures (baseline, Week 4, Week 8): mixed-effects linear models with fixed effects for time, arm, and timexarm interaction; random intercepts for participant.
- Categorical safety outcomes (adverse events): counts and  $\chi^2$  or Fisher's exact tests.

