### **7.2.1 Size of sample**

Allocated as follows:

- o Per cohort: 46 participants
- o Per arm (1:1): 23 participants
- o Expected completers per arm:  $\geq 18$  participants
- o Total completers:  $\geq 72$  participants

This sample size is not powered for definitive hypothesis testing but is sufficient to:

1. Estimate recruitment, retention, and adherence rates with acceptable precision.
2. Generate variance estimates for the primary outcomes (FMA-UE in the Neurological cohort; SPADI in the MSK cohort) to inform sample-size calculations for a future definitive trial.

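### Exploratory aim 3 promises to determine whether combined therapy adds risk, but the only between-arm comparison is a significance test at 23 per arm, which cannot settle that question

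*Protocol*

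**What the plan says.** Protocol section 4.1, Exploratory Aims, item 3, sets the safety aim: "adverse events, overuse symptoms) and determine whether combined therapy introduces any incremental risk".

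The analysis is given in these places:

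- **Planned Statistical Analyses, item 6 (Safety Analyses)** reports "Number and proportion of participants experiencing any AE and serious AE in each arm". It compares the arms by chi-squared test, with events also "descriptively summarised by severity and relatedness".
- **Planned Statistical Analyses, item 3 (Secondary Outcomes, Analysis)** has "Categorical safety outcomes (adverse events): counts and" a chi-squared or Fisher's exact test. Section 5, item 3, says the same.
- **The opening of Planned Statistical Analyses** makes every analysis cohort-specific, by randomised arm, with two-sided tests at 0.05.

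Section 7.2.1 fixes the size: "Per arm (1:1): 23 participants". It then states: "This sample size is not powered for definitive hypothesis testing but is sufficient to" estimate recruitment, retention and adherence rates and supply variance estimates for the primary outcomes. Safety is not on that list.

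The feasibility rates are to carry 95% confidence intervals (Planned Statistical Analyses, item 1; section 5, item 1). The AE comparison has no interval, margin or rule of interpretation.

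**The concern.** To determine whether a treatment adds any risk, a study must be able to tell a real excess of events from none. A test on 23 v 23 does this only when the excess is very large. For any modest true excess the likely outcome is a non-significant p-value, and a p-value alone does not show how large an excess the data still allow. The aim therefore promises more than section 7.2.1 says the sample can deliver.

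At stake is what may be concluded about safety. Section 4.2 expects the results to support or refute routine use, and section 9 describes the system as a research prototype not yet approved for general clinical use. A reader of the final report needs the range of risk differences compatible with the data.

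There is a smaller inconsistency. Item 6 names only the chi-squared test, while item 3 and section 5 also allow Fisher's. With few events the two can give different answers.

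**Working it through.** **Inputs from the protocol.** 23 per arm per cohort (section 7.2.1); 1:1 allocation (section 5); two-sided 0.05 and separate analysis by cohort (Planned Statistical Analyses).

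**Assumed.** AE rates, because the protocol gives none. Control-arm rates from 5% to 20% are shown.

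**1. The plan's own figure.** 23 × 0.8 = 18.4, so at least 18 completers per arm; 4 × 18 = 72 in total. Section 7.2.1 is consistent with itself. It states no power or precision for AEs.

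**2. Power of the planned test.** Exact power is the sum, over all pairs (a, b) that the test rejects, of Bin(a; 23, p1) × Bin(b; 23, p2).

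| Assumed rates | Fisher | Chi-squared (uncorrected) |
|---|---|---|
| 5% v 10% | 2.5% | 7% |
| 10% v 20% | 9% | 16% |
| 20% v 40% | 22% | 32% |
| 10% v 30% | 30% | 41% |
| 10% v 50% | 81% | 88% |

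Hand check for 10% v 20% by normal approximation, with mean rate 0.15:

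- 0.10 × √23 = 0.480
- 1.96 × √(2 × 0.15 × 0.85) = 0.990
- (0.480 − 0.990) / √(0.09 + 0.16) = −1.02, and Φ(−1.02) = 15%

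A true doubling from 5%, 10% or 20% is missed at least 68% of the time, whichever test is used. For 80% power the combined-arm rate would have to reach 36–41% against 5%, 46–50% against 10%, or 60–64% against 20% (chi-squared to Fisher).

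**3. Size needed for 80% power at 10% v 20%.** n = (0.990 + 0.842 × √0.25)² / 0.10² = (1.411)² / 0.01, about 199 per arm. Pooling the cohorts (46 per arm), which is not planned, would still give only 18% to 28%.

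**4. What an interval would show.** Suppose 5/23 (21.7%) v 2/23 (8.7%), a difference of 13.0 points. The Wilson limits are 9.7% to 41.9% and 2.4% to 26.8%. Newcombe's interval is then:

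- lower: 0.130 − √[(0.217 − 0.097)² + (0.268 − 0.087)²] = −0.087
- upper: 0.130 + √[(0.419 − 0.217)² + (0.087 − 0.024)²] = +0.342

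So the difference is +13 points (95% CI −9 to +34), with p = 0.41 (Fisher) or 0.22 (chi-squared). The test is non-significant, yet an excess of 34 points is not excluded. Equal counts leave similar room: 2/23 v 2/23 gives 0 (−19 to +19), and 5/23 v 5/23 gives 0 (−24 to +24).

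**5. No events.** For 0/23 the exact two-sided 95% upper limit is 1 − 0.025^(1/23) = 14.8%.

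**6. Choice of test.** With equal arms the expected events per arm are half the total, so they fall below 5 when there are fewer than 10 events in all. For 4/23 v 0/23 (expected 2 per arm), uncorrected chi-squared gives p = 0.036 and Fisher gives p = 0.109.

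**The case against.** The strongest reply is that the limitation is already disclosed. The aim is labelled exploratory, its sentence opens with a verb of assessment, the study is called a pilot, and section 7.2.1 disclaims definitive testing. Sample-size sections do not usually list exploratory aims, so the absence of safety from that list is weak evidence on its own. All of this stands and limits the severity. It does not remove the promise to determine added risk; the disclaimer is the text with which that promise conflicts.

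Second, the safety plan is more than a p-value. AEs are recorded at every session and by checklist at Weeks 4, 8 and 12, then summarised by severity and relatedness, and an independent Data Monitoring Committee reviews them at mid-point. This also stands, though none of it yields an estimate of the arm difference with its uncertainty.

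Third, the interval method could be left to a statistical analysis plan. That is fair as regards the choice of interval. But the protocol itself fixes both the aim and the comparison, and the two do not match.

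A reader might infer that the sponsor will report a non-significant test as showing no added risk. No section says so; the pairing of the aim with a test only leaves the door open. A reader might also infer that the serious-AE analysis is bound to an invalid chi-squared test. That is not supported either: item 3 and section 5 already allow Fisher's, and no serious-AE rate is given.

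**Conclusion.** The concern holds as a mismatch between the wording of one exploratory aim and what the stated comparison can show at 23 per arm. Under the assumed rates the test detects 10% v 20% about 9% to 16% of the time and 10% v 30% about 30% to 41% of the time. Only an excess of roughly 31 to 44 points over a control rate of 5% to 20% would be found with 80% power. A non-significant result could not support a conclusion of no added risk.

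The exact percentages depend on the assumed rates, but low power for a doubling holds at every control rate tried. It does not depend on which total is used either. Section 7.2 also mentions 108 participants, or 108 / 4 = 27 per arm if split equally; by the normal approximation even 46 per arm gives only 27% for 10% v 20%.

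Severity is minor: no calculation in the protocol is wrong, the aim is exploratory, and other safety oversight is planned.

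**What to change.** - **Section 4.1, exploratory aim 3:** replace the promise to determine added risk with an aim to *estimate the difference between arms in adverse-event and overuse-symptom rates*.
- **Planned Statistical Analyses, item 6:** make the per-cohort risk difference with its 95% CI (Newcombe's, for example) the main comparison for any AE and for serious AEs. Give the exact upper limit when an arm has no events.
- **If a test is kept:** bring item 6 into line with item 3 and section 5 by naming Fisher's exact test for sparse counts.
- **Interpretation:** add one sentence saying that a non-significant difference is not evidence of no added risk.

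The cost is wording in the protocol and any analysis plan. Sample size, visits and data collection do not change. The downside is a less ambitious safety aim, which is what this sample can support.

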## Feasibility Objectives

- Estimate **recruitment rate, retention rate, and data completeness** for each arm and cohort.
- Evaluate the acceptability of randomisation into **Combined ReHabGame + usual care** versus **usual care alone**.
- Generate preliminary estimates of **variance** in primary outcomes to inform sample-size calculations for a definitive trial.

## 4.2 Outcome

**Broad Outcome:** A clearer understanding of how a markerless, game-based rehabilitation system affects upper-limb motor recovery, motivation, and overall functional independence.

**Practical Impact:** Evidence to support (or refute) the use of ReHabGame as a routine therapeutic tool, potentially informing clinical guidelines and future technology-driven rehabilitation strategies.

After each gamified rehabilitation session, participants will receive personalised, visual performance feedback generated by the ReHabGame platform. This includes:

- A PDF-based summary showing:
  - Percentage of movement types (e.g. abduction, adduction of the upper arm)
  - Distribution of virtual objects around the participant in the game environment
  - Visual markers of target reach, joint usage, and task completion
- Feedback is presented immediately post-session in a simple, colour-coded format that participants can understand without technical expertise.

A member of the research team will review this feedback in person with the participant to:

- Celebrate progress and encourage engagement
- Clarify what the data means in lay terms
- Address any confusion or concern
- Adjust future gameplay settings if needed to support optimal challenge and safety

The ReHabGame system uses an **automated, performance-based algorithm** to dynamically adjust the difficulty level of gameplay in real time. This ensures that exercises remain **appropriately challenging, engaging, and within the user's capabilities**, thereby reducing frustration and promoting sustained participation.

### Difficulty Adjustment Logic

- At each session, the system spawns **three interactive virtual objects** within the participant's reach zone.
- The participant's ability to successfully **interact with or complete tasks involving these objects** determines the next session's difficulty level.
  - If the participant is **unable to interact with all three objects**, the difficulty is **automatically reduced to Level 0**, providing a simplified task setup with wider target zones and reduced motion requirements.
  - If the participant completes the interactions successfully, the difficulty level is **increased incrementally up to Level 5**, which includes:
    - Increased object speed
    - Reduced object size
    - More complex trajectories
    - More demanding spatial configurations

This **fuzzy logic-based scaling** allows for a responsive system that adjusts to moment-to-moment motor performance, thereby personalising therapy without requiring therapist intervention.

**No remote questionnaires or feedback sessions will be conducted unless the participant explicitly prefers to complete their follow-up session online.**

## 5 STUDY DESIGN and METHODS of DATA COLLECTION AND DATA ANALYSIS

Type: Parallel, two-cohort (Neurological vs MSK), two-arm randomized controlled trial

- Arms (within each cohort):
  1. Usual-care physiotherapy only
  2. Combined ReHabGame + usual-care

Allocation: 1:1 randomisation, stratified by baseline severity (high vs low) within each cohort

- Blinding:
  - Outcome assessors blinded to group assignment

- Participants & therapists unblinded (interventions are overt)
- Duration: 6–8 weeks of intervention (2 sessions/week) + 4-week follow-up
- Sample size: 23 per arm per cohort (46 per cohort; 92 total), allowing ≈20% attrition.

Domain	Instrument & Timing
Demographics & History	Structured questionnaire at Week 0 (age, sex, diagnosis, time since onset/surgery, comorbidities)
Primary Outcomes	- Neurological: Fugl–Meyer Assessment (upper extremity) at Weeks 0, 8- MSK: SPADI at Weeks 0, 8
Secondary Outcomes	- Neurological: Barthel Index at Weeks 0, 8- MSK: DASH, pain VAS, goniometric ROM at Weeks 0, 8
Interim Metrics	At Week 4 for all: SUS, engagement survey, adverse-event checklist, quick FMA-UE subset (neuro) or SPADI re-test (MSK), Kinect snapshot metrics
Follow-up Metrics	At Week 12: SUS, engagement survey, adverse-event update, optional brief functional check
Motion-Tracking Data	Automatically logged each session via Kinect: range of motion, smoothness (jerk), repetition count, completion time, accuracy
Session Adherence	PDF session log (date, duration, pain VAS, issues) maintained by participant; automatically generated session report PDFs summarising movement metrics
Qualitative Feedback	Semi-structured interview or written feedback at end of Week 8 (usability, barriers, facilitators, motivation)
Safety Monitoring	Adverse events recorded at every session and via AE checklist at Weeks 4, 8, 12; severity and relatedness noted

All analyses conducted separately within each cohort on an intention-to-treat basis,  $\alpha = 0.05$  two-sided.

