### 3. Intervention Sessions (Weeks 1–8): Questionnaire at week 2, 4, 8 (**via the above Link**)

- Combined arm only; 2x/week, Weeks 1–8

Usual care only:

- o 30–45 min therapist-led physiotherapy per session
- o 2 sessions/week for 6–8 weeks (standardised protocol)
- **Combined care- Usual-care + ReHabGame:**
  - o 30–45 min Kinect-guided exercises per session.
  - o Real-time difficulty adaptation; metrics auto-logged.
  - o Both modalities, each 2x/week (on separate days or back-to-back).
  - o Each session is logged in the PDF format.

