### 3. Secondary & Repeated-Measures Analyses

- **Continuous outcomes** (Barthel, DASH, Pain VAS, ROM, SUS, engagement scores):
  - ANCOVA at Week 8 as above
  - **Mixed-effects linear models** for repeated measures (Weeks 0, 4, 8) with fixed effects for time, arm, and timexarm; random intercepts for participants
- **Categorical safety outcomes:** AE counts compared via  $\chi^2$  or Fisher's exact tests

4. **Motion-Tracking Metrics**
  - o Compare mean ROM, smoothness, completion time, and accuracy at Weeks 4 and 8 using ANCOVA, adjusting for baseline Kinect metrics
5. **Exploratory Analyses**
  - o **Cost/resource use:** descriptive comparison of therapist time and equipment costs per participant (t-tests or nonparametric equivalents)
  - o **Qualitative data:** thematic analysis of interviews to identify barriers/facilitators; representative quotes to illustrate key themes
6. **Missing Data**
  - o **< 5% missing:** complete-case analysis
  - o **≥ 5% missing:** multiple imputation by chained equations (20 datasets) including baseline covariates and outcomes
  - o **Sensitivity:** per-protocol analysis (≥ 75% sessions attended)
7. **Safety Review**
  - o AE rates summarised by arm; reviewed by an independent Data Monitoring Committee at midpoint (after ~50% complete)

All statistical programming and reporting will be done in R ( $\geq 4.0$ ), with scripts version-controlled for reproducibility.

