## Staff Training

- Staff at both sites will receive a brief orientation on ReHabGame's operation, the motion-tracking sensors, and participant safety protocols.
- Any site-specific health and safety training required by hospital policy (e.g., manual handling, infection control) must be completed by the research team.

1. Identification & Recruitment
  - At each site, clinical teams (physiotherapists, occupational therapists, rehab consultants) will introduce the study to eligible patients and, if they express interest, refer them to the research team for formal screening.
  - Potential participants will receive an information sheet and have an opportunity to ask questions before providing written informed consent.
2. Baseline Assessments
  - Participants will undergo baseline clinical evaluations (e.g., Fugl-Meyer Assessment), and relevant questionnaires.
  - These may take place in a private clinic room or dedicated rehabilitation space.
3. ReHabGame Intervention
  - Participants will use ReHabGame in designated therapy areas equipped with the Kinect hardware.
  - Session frequency and duration will follow the study protocol (e.g., 1–2 sessions per week over 6–8 weeks).
  - Research staff or designated clinical staff will supervise sessions, ensuring correct usage and participant safety.
4. Data Collection
  - Quantitative: System logs (range of motion, frequency of play), standardized clinical scales (pre-/post-intervention).
  - Qualitative: Questionnaire to gather feedback on user experience and feasibility.
5. Follow-Up Assessments
  - Post-intervention evaluations will be conducted to assess changes in upper-limb function and gather final feedback.
  - Data will be entered into secure, password-protected electronic databases, ensuring confidentiality and compliance with data protection laws.

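### The by-arm adverse event comparison cannot separate added risk from more frequent asking, because the combined arm has about 1.5 to 2 times the sessions at which events are recorded

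*Protocol*

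**What the plan says.** **Recording.** The Safety Monitoring row of the table in Section 5 states: "Adverse events recorded at every session and via AE checklist at Weeks 4, 8, 12; severity and relatedness noted". The checklist schedule is the same in both arms.

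**Sessions.** Under Study Timeline and Procedures, item 3, usual care is "2 sessions/week for 6–8 weeks (standardised protocol"). Combined care is "Both modalities, each 2x/week (on separate days or back-to-back"). In Section 6, Staff Training, the ReHabGame item reads: "Session frequency and duration will follow the study protocol (e.g., 1–2 sessions per week over 6–8 weeks").

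**Endpoint and test.** Planned Statistical Analyses, item 6, reports "Number and proportion of participants experiencing any AE and serious AE in each arm", with "Comparison by arm via" χ² tests. The secondary-outcome analyses under Planned Statistical Analyses (item 3) and in Section 5 (item 3) both allow χ² or Fisher's exact test. The Section 5 text has "AE counts compared via" those tests.

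**Purpose.** Exploratory aim 3 in Section 4.1 is to assess safety outcomes, including overuse symptoms, and "determine whether combined therapy introduces any incremental risk". An independent Data Monitoring Committee reviews safety data at the mid-point, and Section 5 has AE rates summarised by arm for that review.

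The protocol does not limit the comparison to the common checklists, relate events to sessions attended, or separate session-recorded from checklist-recorded events.

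**The concern.** The proportion of participants with any recorded event depends on how often events happen and on how often someone asks. The two arms differ in the second by design. The likely events are minor ones: Section 8.1 expects mild fatigue or discomfort, and exploratory aim 3 names overuse symptoms. Such events are reported more readily when people are asked often. Section 4.2 adds an in-person review with a member of the research team after each ReHabGame session, partly to deal with any concern, which is a further prompt in one arm only. Participants and therapists are unblinded.

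An excess in the combined arm could therefore reflect real extra risk, more frequent asking, or both. The planned test returns one p-value for the mixture, while the stated aim is to judge incremental risk. The monitoring committee would see the same mixture at mid-point.

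**Working it through.** **Inputs.** Usual care: 2 sessions a week for 6–8 weeks. ReHabGame: 2 a week (intervention timetable) or 1–2 a week (Staff Training). Checklists: 3 in each arm. Sample: 23 per arm per cohort. The protocol states no AE rate and no probability that a contact picks up an event.

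**Step 1: the plan's own figure.** The only stated figure that bears on the comparison is the sample. 23 × 0.80 = 18.4, so at least 18 completers per arm, and 4 × 18 = 72 in total. This reproduces Section 7.2.1.

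**Step 2: recording occasions.**

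| | Usual care | Combined, ReHabGame 2/week | Combined, ReHabGame 1/week |
|---|---|---|---|
| Sessions, 6 weeks | 2 × 6 = 12 | 4 × 6 = 24 | 3 × 6 = 18 |
| Sessions, 8 weeks | 2 × 8 = 16 | 4 × 8 = 32 | 3 × 8 = 24 |
| Ratio to usual care | – | 2.0 | 1.5 |
| Sessions + 3 checklists | 15–19 | 27–35 | 21–27 |
| Ratio to usual care | – | 1.80–1.84 | 1.40–1.42 |

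If ReHabGame is given twice a week, always back-to-back with usual care, there are 12–16 contact days in both arms. The ratio is then 1.0 if events are asked about once per visit.

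**Step 3: the effect of asking alone.** Hold the underlying weekly events equal in both arms. Let each contact in the week capture an event with probability s, independently (an assumption). With m contacts a week, capture = 1 − (1 − s)^m.

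| s | m = 2 | m = 4 | Ratio 4 vs 2 | m = 3 | Ratio 3 vs 2 |
|---|---|---|---|---|---|
| 0.30 | 0.510 | 0.760 | 1.49 | 0.657 | 1.29 |
| 0.50 | 0.750 | 0.938 | 1.25 | 0.875 | 1.17 |
| 0.70 | 0.910 | 0.992 | 1.09 | 0.973 | 1.07 |
| 0.90 | 0.990 | 1.000 | 1.01 | 0.999 | 1.01 |

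These are ratios of captured events. The ratio of participants with any event is no larger, because a person with several captured events counts once.

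**Step 4: allow for the common checklists.** Suppose, for illustration only, that a checklist recovers half of what sessions missed: capture + 0.5 × (1 − capture).
- s = 0.30: 0.510 + 0.245 = 0.755 against 0.760 + 0.120 = 0.880, ratio 1.17.
- s = 0.50: 0.750 + 0.125 = 0.875 against 0.938 + 0.031 = 0.969, ratio 1.11.

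**Step 5: expected counts.** With 23 per arm and overall event proportion p, the expected number with an event in each arm is 23p. This is below 5 when p < 5/23 = 0.217.

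**The case against.** **Extra sessions are part of the treatment, so extra events may be real.** This stands, and it rules out a tempting calculation. A reader might give every session the same 2% chance of a recorded event and use 1 − (1 − 0.02)^n. That gives 22–28% with any event in usual care (12–16 sessions) against 38–48% in the combined arm (24–32 sessions), and one might call this a difference with no true risk behind it. The protocol does not support that label. If sessions themselves cause fatigue or discomfort, doubling them raises the participant's true risk, which is what exploratory aim 3 asks about. For the same reason, the χ² rejection rates of 15–44% that this model gives at 23 per arm (1–5% per session) are not false-positive rates for participant-level risk.

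**Back-to-back delivery removes the extra asking.** Partly. The protocol permits it but does not require it, and Section 5 says every session.

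**Repeated events in one person are treated as independent.** A reader might infer this from the Section 5 wording on AE counts. Planned Statistical Analyses, item 6, defines the endpoint as participants with any event, which largely settles it. What remains is loose wording.

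**The source of the events tested is left open.** True. No section says outright that session and checklist reports are merged, and an analysis plan could settle it. But the protocol itself fixes the recording scheme, endpoint and test, and as written any AE would include both sources.

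**Safety is an exploratory aim in a pilot.** Section 7.2.1 says the trial is not powered for definitive testing, and events are also summarised by severity and relatedness. This limits the weight of the point but does not remove it.

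**Conclusion.** The concern holds in a limited form. The combined arm has about 1.5 to 2 times the sessions at which AEs are recorded, so its any-AE proportion is expected to be raised partly by more frequent asking. The planned comparison cannot separate that from true incremental risk. The direction follows from the design; the size does not.

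With equal underlying events and independent capture at each contact, the inflation at four contacts against two runs from 1.01 (90% captured per contact) to 1.49 (30%). It is smaller with three contacts, smaller once checklists recover missed events, and close to none if sessions are back-to-back and asked about once. These capture probabilities are assumptions, since the protocol gives none.

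A reader might conclude that any excess in the combined arm would be an artefact, or that session records should be dropped from the comparison. Neither follows: an excess could be genuine, and session records are the better source for minor overuse events.

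**What to change.** - **Keep** per-session recording and the all-source AE table. Flag the source of each event (session or checklist) and show sessions attended by arm beside the table.
- **Add** a between-arm comparison of participants with at least one event on the Week 4, 8 and 12 checklists, as a risk difference with exact 95% CI. Both arms then have three scheduled occasions. Read incremental risk from both tables.
- **Report** all serious events whatever their source, and give the monitoring committee both tables.
- **Test wording:** in Planned Statistical Analyses, item 6, use Fisher's exact test where expected counts are below 5 (overall event proportion under about 22% at 23 per arm). This matches the option already given in the two secondary-outcome analyses.
- **Unit:** in Section 5, item 3, replace AE counts with participants with at least one AE.
- **Reconcile** the ReHabGame frequency in the intervention timetable with that under Staff Training.

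**Cost.** One source field on the AE record (Section 5 does not say that source is captured), one extra table and a few wording changes. The checklist comparison relies on recall over about four weeks and may miss minor events, which is why the all-source table stays. It equalises the number of scheduled checklist occasions, but it does not remove reporting differences that arise because participants know their arm.
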